On 15 April 2020, all 7 subjects were more than 1 week outside of the visit window for their next dose or for the Day 71 visit and there was no indication that the site would be able to re-open within the following 2 weeks. In order to ensure subject safety and protect data integrity, Endo, in accordance with the *FDA Guidance on Conduct of Clinical Trials of Medical Products during COVID-19 Public Health Emergency* (March 2020, updated 16 April 2020), decided to add additional subjects and modify the assessments required for current subjects when the investigational site re-opens as follows (and with subject consent):

- Subjects who were in screening for the study at the time of interruption (18 March 2020) but who had not been dosed with CCH will repeat all screening assessments to determine eligibility, if willing to do so. All screening assessments must be repeated within the screening window.
- Subjects who had received less than 3 doses of CCH prior to 18 March 2020 will be allowed to continue in the study and may receive any remaining doses with Sponsor approval. These subjects will complete all remaining visits and assessments EXCEPT biopsies and biopsy follow-up visits, if willing to do so. These subjects will be included in the safety assessments for the study, but will not be included in the efficacy assessments. Subjects who received less than 3 doses prior to 18 March 2020 may elect to remain in the study without receiving additional doses.
- Subjects who received all 3 doses of CCH prior to 18 March 2020, will be allowed to continue in the study and complete all remaining visits and assessments (including biopsies and biopsy follow-up visits), if willing to do so. These subjects will be included in the safety assessments for the study, but will not be included in the efficacy assessments. Subjects who received all 3 doses of CCH prior to 18 March 2020 may elect to remain in the study without completing the biopsies and biopsy follow-up visits.

- An additional 12 subjects will be dosed in the study. These subjects will be included in the safety assessments, and all efficacy assessments will be based on the data for these 12 subjects.

Major updates to specific sections of the protocol that are impacted are outlined below, other minor changes that do not impact study conduct or participant safety were also made:

Section 1.1 Synopsis

Study Period: The estimated date of last subject completion has been changed from November 2020 to October 2021.

Overall Design: The number of subjects to be dosed in the study has been increased from 12 to 19. The subject participation has been updated as outlined above. The approximate duration of the study has been increased from 12 months to 24 months. The per subject duration of participation has been modified to indicate approximately 305 days (10 months) plus any delays due to the COVID-19 public health emergency.

Number of Subjects (planned): Wording has been modified to indicate that approximately 19 subjects will receive study drug so that approximately 12 subjects who did not experience interruptions due to the COVID-19 public health emergency will complete the study.

Section 1.2 Schedule of Activities

Footnote “[j](#)” has been amended and added to indicate that subjects who had less than 3 doses of CCH prior to 18 March 2020 will not have the Day 71 or Day 251 biopsies. And footnote “[k](#)” was added to indicate subjects who had less than 3 doses of CCH prior to 18 March 2020 will not be required to have the Day 85 and Day 265 biopsy follow-up visits.

Section 2.1 Study Rationale

The rationale for changes to the study due to the COVID-19 public health emergency (as outlined above) has been added to the end of this section.

Section 4.1 Overall Design

The section has been updated with the modifications in design for subjects who were screened or dosed prior to 18 March 2020 as outlined above.

Section 4.4 End of Study Definition

This section has been modified as follows: A subject will be considered to have completed the study if the subject received their first dose of study drug after 18 March 2020 and completed the Day 265 visit. Subjects who received their first dose of study drug prior to 18 March 2020 and complete the Day 265 Visit (or the Day 251 Visit if they elect not to have biopsies) also will be considered to have completed the study.

Section 5.4 Screen Failures

The following text was added: Subjects who were screened prior to 18 March 2020 for the study but had not been dosed with CCH may be rescreened. All screening assessments must be repeated within the screening window (35 days).

Section [6.1](#) Selecting the Treatment Region

The following text was added: For the 12 new subjects who receive their first dose of study drug after 18 March 2020, every attempt will be made to enroll an equal number of subjects across the 2 severity levels in both buttocks and thighs (eg, 3 subjects with moderate buttock cellulite, 3 subjects with severe buttock cellulite, 3 subjects with moderate thigh cellulite, and 3 subjects with severe thigh cellulite).

Section [7.1](#) Discontinuation of Study Treatment, Section [7.2](#) Subject Discontinuation/Withdrawal from Study, and Section [7.3](#) Lost to Follow-up

These sections have been modified to indicate that all subjects dosed prior to 18 March 2020 will be replaced. In addition, subjects who receive their first dose of study drug after 18 March 2020 and subsequently discontinue from study treatment and/or withdraw from the study and/or are lost to follow-up will not be replaced.

Section [8.2.9](#) Biopsy Follow-up Examination

This section was updated to indicate that the Day 85 and Day 265 Biopsy Follow-up Visits are not required for subjects who had less than 3 doses of study drug prior to 18 March 2020.

Section [8.6.2](#) Double Punch Biopsy

This section was updated to indicate that subjects who had less than 3 doses of study drug prior to 18 March 2020 will not have the Day 71 and Day 251 biopsies performed. In addition, subjects who completed 3 doses of CCH prior to 18 March 2020 will have Day 71 or Day 251 biopsies, if willing to do so.

Section [9.2](#) Populations for Analysis

The Evaluable Population has been redefined to include all subjects in the Safety Population who received their first dose of CCH in this study after 18 March 2020 and who had a baseline and at least 1 postinjection PR-PCSS evaluation.

Section [9.3.1](#) Efficacy Analysis

This section has been updated to indicate that all secondary and tertiary PR-PCSS, CR-PCSS, and Hexsel efficacy endpoints will be summarized by treatment area (left or right) and region (buttock or thigh) using appropriate descriptive statistics using the Evaluable Population.

Section [9.4](#) Interim Analysis

This section has been modified to indicate that the interim analysis will be conducted when at least 4 of the 12 subjects who received their first dose of study drug after 18 March 2020 have completed their Day 71 visit. For all subjects who received their first dose of study drug after 18 March 2020, analysis of all primary, secondary, and tertiary endpoints will be included in the interim analysis. For the subjects who received all three doses prior to 18 March 2020, their MRI and biopsy data, if available, will be assessed separately but included in interim analysis. The purpose of the interim analysis is to determine if changes in morphology and/or histology can be identified using MRI and biopsy. If the interim analysis does not indicate that such changes can be identified, subsequent or additional MRIs or biopsies will not be performed in this study.

Protocol Amendment 2: 04 March 2020

Amendment 2 was incorporated into the protocol on 04 March 2020. The major reason for this amendment is that a slower than expected enrollment rate has made it unlikely that all subjects will complete the Day 71 visits before the earliest enrolled subjects are scheduled for additional MRI and biopsies. Therefore, the interim analysis will be conducted when the first 6 subjects complete their Day 71 Visit, rather than when all subjects complete that visit. Additional minor changes that do not impact study conduct or participant safety were also made.

The major revision to the protocol is:

- The interim analysis will be done when at least 6 subjects have completed their Day 71 visit (Section 9.4).

Protocol Amendment 1: 16 January 2020

Amendment 1 was incorporated into the protocol on 16 January 2020. The major reason for this amendment is to allow more time to obtain evaluable MRI images at screening and to permit repetition of MRIs during screening. Additional minor changes that do not impact study conduct or participant safety were also made.

The major revisions to the protocol include:

- Increasing the window for screening from 28 to 35 days. The screening period is now Day -35 to Day -1. This increases the duration of subject participation from approximately 298 Days to approximately 305 days (Section 1.1 Synopsis, Section 1.2 Schedule of Activities, and Section 4.1 Overall Design).
- Increased the window for the Day 71 visit to 10 days (Section 1.2 Schedule of Activities).

1. PROTOCOL SUMMARY

1.1. Synopsis

Name of Sponsor/Company: Endo Pharmaceuticals Inc. Name of Investigational Product: CCH Name of Active Ingredient: Collagenase clostridium histolyticum																	
Title of Study: A Phase 2a open-label, study to assess the impact of CCH treatment of buttock and thigh cellulite in adult females using photonumeric scales, magnetic resonance imaging, and histopathology																	
Lead Principal Investigator: Not applicable																	
Study Period: Estimated date first subject enrolled: November 2019 Estimated date last subject completed: October 2021	Phase of Development: 2a																
Objectives and Endpoints: 
  
 Objectives	Endpoints	
   
 Primary		
 
  
 To assess the subject reported impact of CCH in the treatment of cellulite in adult females. 	 
 The change from baseline (screening) in Patient-reported Photonumeric Cellulite Severity Scale (PR-PCSS) at Day 71. 	
 
 Secondary		
 
  
 To assess the subject and clinician reported impact of CCH in the treatment of cellulite in adult females. 	 
 The change from baseline (screening) in PR-PCSS at Days 22 and 43. The change from baseline (screening) in Clinician-reported Photonumeric Cellulite Severity Scale (CR-PCSS) at Days 22, 43, and 71. The change from baseline (screening) in Hexsel Cellulite Severity Scale (CSS) at Days 22, 43, and 71. 	
 
  
 To radiologically assess the impact of treatment with CCH in adult females with cellulite. 	 
 Comparison of baseline (screening) MRI tissue morphology and septae under the treatment areas to images taken at Day 71. 	
 
  
 To evaluate tissue histopathology to assess the impact of treatment with CCH in adult females with cellulite. 	 
 Comparison of baseline (screening) histopathology to the histopathology of samples taken at Day 71. 	
 
  
 To assess the safety of CCH treatment of cellulite in adult females. 	 
 The proportion of subjects reporting each adverse event, treatment-emergent adverse event, adverse event of special interest, and serious adverse event. The change from baseline in vital signs and clinical laboratory parameters at each visit where these parameters are measured. The change from baseline in anti-AUX-I and anti-AUX-II antibodies and neutralizing antibodies at each visit where these parameters are measured. 	
  
		Objectives	Endpoints	Primary		
 To assess the subject reported impact of CCH in the treatment of cellulite in adult females. 	
 The change from baseline (screening) in Patient-reported Photonumeric Cellulite Severity Scale (PR-PCSS) at Day 71. 	Secondary		
 To assess the subject and clinician reported impact of CCH in the treatment of cellulite in adult females. 	
 The change from baseline (screening) in PR-PCSS at Days 22 and 43. The change from baseline (screening) in Clinician-reported Photonumeric Cellulite Severity Scale (CR-PCSS) at Days 22, 43, and 71. The change from baseline (screening) in Hexsel Cellulite Severity Scale (CSS) at Days 22, 43, and 71. 	
 To radiologically assess the impact of treatment with CCH in adult females with cellulite. 	
 Comparison of baseline (screening) MRI tissue morphology and septae under the treatment areas to images taken at Day 71. 	
 To evaluate tissue histopathology to assess the impact of treatment with CCH in adult females with cellulite. 	
 Comparison of baseline (screening) histopathology to the histopathology of samples taken at Day 71. 	
 To assess the safety of CCH treatment of cellulite in adult females. 	
 The proportion of subjects reporting each adverse event, treatment-emergent adverse event, adverse event of special interest, and serious adverse event. The change from baseline in vital signs and clinical laboratory parameters at each visit where these parameters are measured. The change from baseline in anti-AUX-I and anti-AUX-II antibodies and neutralizing antibodies at each visit where these parameters are measured.
Objectives	Endpoints																
Primary																	

 To assess the subject reported impact of CCH in the treatment of cellulite in adult females. 	
 The change from baseline (screening) in Patient-reported Photonumeric Cellulite Severity Scale (PR-PCSS) at Day 71. 																
Secondary																	

 To assess the subject and clinician reported impact of CCH in the treatment of cellulite in adult females. 	
 The change from baseline (screening) in PR-PCSS at Days 22 and 43. The change from baseline (screening) in Clinician-reported Photonumeric Cellulite Severity Scale (CR-PCSS) at Days 22, 43, and 71. The change from baseline (screening) in Hexsel Cellulite Severity Scale (CSS) at Days 22, 43, and 71. 																

 To radiologically assess the impact of treatment with CCH in adult females with cellulite. 	
 Comparison of baseline (screening) MRI tissue morphology and septae under the treatment areas to images taken at Day 71. 																

 To evaluate tissue histopathology to assess the impact of treatment with CCH in adult females with cellulite. 	
 Comparison of baseline (screening) histopathology to the histopathology of samples taken at Day 71. 																

 To assess the safety of CCH treatment of cellulite in adult females. 	
 The proportion of subjects reporting each adverse event, treatment-emergent adverse event, adverse event of special interest, and serious adverse event. The change from baseline in vital signs and clinical laboratory parameters at each visit where these parameters are measured. The change from baseline in anti-AUX-I and anti-AUX-II antibodies and neutralizing antibodies at each visit where these parameters are measured. 																

Name of Sponsor/Company: Endo Pharmaceuticals Inc. Name of Investigational Product: CCH Name of Active Ingredient: Collagenase clostridium histolyticum	
Objectives	Endpoints
Tertiary	

 To assess the complete loss of patient reported impact after CCH treatment in adult females with cellulite. To assess the complete loss of clinician reported impact after CCH treatment in adult females with cellulite. To radiologically assess the long-term impact of treatment with CCH in adult females with cellulite. To evaluate tissue histopathology to assess the long-term impact of treatment with CCH in adult females with cellulite. 	
 The proportion of subjects with no change (or worsening) from baseline (screening) in PR-PCSS rating at Day 161 and at Day 251. The proportion of subjects with no change (or worsening) from baseline (screening) in CR-PCSS rating at Day 161 and at Day 251. The proportion of subjects with no change (or worsening) from baseline (screening) in Hexsel CSS total score at Day 161 and at Day 251. Comparison of baseline (screening) magnetic resonance imaging (MRI) tissue morphology and septae under the treatment areas to images taken at Day 251. Comparison of baseline (screening) histopathology to the histopathology of samples taken at Day 251.
Overall Design: 
This is a single-center, open-label, Phase 2a study to assess the photonumeric scale, morphological, and histopathological changes associated with CCH in adult women with moderate or severe edematous fibrosclerotic panniculopathy (EFP). Approximately 19 subjects with moderate or severe EFP in the posterolateral thighs will be dosed in this study.
 
This study was suspended due to the COVID-19 public health emergency on 18 March 2020. When the study re-opens, subjects who had received less than 3 doses of CCH prior to 18 March 2020 will be allowed to continue in the study and may receive any remaining doses with Sponsor approval. These subjects will complete all remaining visits and assessments EXCEPT biopsies and biopsy follow-up visits, if willing to do so. These subjects will be included in the safety assessments for the study, but will not be included in the efficacy assessments. Subjects who received less than 3 doses prior to 18 March 2020 may elect to remain in the study without receiving additional doses.
 
Subjects who received all 3 doses of CCH prior to 18 March 2020, will be allowed to continue in the study and complete all remaining visits and assessments (including biopsies and biopsy follow-up visits), if willing to do so. These subjects will be included in the safety assessments for the study, but will not be included in the efficacy assessments. Subjects who received all 3 doses of CCH prior to 18 March 2020 may elect to remain in the study without completing the biopsies and biopsy follow-up visits.
 
An additional 12 subjects will be dosed in the study. These subjects will be included in the safety assessments, and all efficacy assessments will be based on the data for these 12 subjects. For the 12 subjects who receive their first dose of study drug after 18 March 2020, every attempt will be made to enroll an equal number of subjects across the 2 severity levels in both buttocks and thighs (eg, 3 subjects with moderate buttock cellulite, 3 subjects with severe buttock cellulite, 3 subjects with moderate thigh cellulite, and 3 subjects with severe thigh cellulite).
	

Name of Sponsor/Company: Endo Pharmaceuticals Inc.
Name of Investigational Product: CCH
Name of Active Ingredient: Collagenase clostridium histolyticum
Following a screening period of up to 35 days, qualified subjects will receive 0.84 mg of CCH per treatment area (each buttock or each thigh) for a total dose of 1.68 mg in both buttocks or both thighs per treatment session \times 3 treatment sessions (Day 1, Day 22, and Day 43). Buttock treated subjects will receive 0.84 mg of CCH administered as up to 12 injections (0.3 mL administered as three 0.1 mL aliquots per injection in each buttock). Thigh treated subjects will receive 0.84 mg of CCH administered as up to 12 injections (1.5 mL administered as five 0.3 mL aliquots per injection in each thigh).
Subjects will have MRI and (except as noted above) double punch biopsies of 3 selected target dimples 3 times during the study. All subjects will be followed for 265 days after the first dose of study treatment.
Subjects will participate in the study for approximately 305 days (10 months) plus any delays caused by the COVID-19 public health emergency. The duration of the study from first subject first visit to last subject last visit will be dependent upon the ability of the site to identify and enroll subjects. The entire study is expected to require about 24 months to complete.
Disclosure Statement: This is an open-label study.
Number of Subjects (planned): Approximately 19 subjects will receive study drug so that approximately 12 subjects who did not experience COVID-19 public health emergency interruption will complete the study.
Treatment Groups and Duration: Subjects will receive 3 treatment sessions 21 days apart and consisting of 0.84 mg of CCH in each treatment area (each buttock or each thigh for a total dose of 1.68 mg). The total amount of CCH to be administered per subject over the course of the study will not exceed 5.04 mg.
Data and Safety Monitoring Committee: No data and safety monitoring committee will be used for this study.

1.2. Schedule of Activities

Table 1: Schedule of Activities

Activities	Screening (Day -35 to Day -1)			Treatment Phase			Extension Phase			
	Before MRI	Before biopsy	Approximately Day -14	Day 1 Treatment Session I	Day 22 (± 3 Days) Treatment Session II	Day 43 (± 3 Days) Treatment Session III	Day 71 (+10 Days)	Day 85 (± 5 Days)/ Biopsy Follow-up	Day 161 (± 15 Days)	Day 251 (± 15 Days)/ Early Termination
Informed consent ^a	X									
Inclusion/exclusion criteria review ^b	X			X						
Medical and surgical history	X									
EFP history	X									
Prior medications (including all prior medications for cellulite)	X									
Physical examination	X									
Height	X									
Weight	X			X	X	X	X	X	X	X
Fitzpatrick Skin Type	X									
Vital signs	X			X ^c	X ^c	X ^c	X	X	X	X
ECG	X									
Hematology, chemistry, and urinalysis	X						X			X
Serum pregnancy test	X									
Urine pregnancy test				X	X	X	X ^d	X	X ^d	
HIV and Hepatitis B tests	X									
Immunogenicity sample collection				X			X	X	X	X
Selection of treatment region (both buttocks or both thighs)	X									
Imaging for efficacy assessments (IntelliStudio)	X ^c			X ^t	X ^t	X ^t	X	X	X	X
PR-PCSS	X ^c				X	X	X	X	X	X
CR-PCSS	X ^c				X	X	X	X	X	X
Hexsel CSS	X ^c				X	X	X	X	X	X
Selection, marking, labeling, and/or photography of 3 dimples for MRI and Biopsy (Dimples 1, 2, and 3)		X								

[figure not shown]

Table 1: Schedule of Activities (Continued)

Activities	Screening (Day -35 to Day -1)			Treatment Phase			Extension Phase				
	Before MRI	Before biopsy	Approximately Day -14	Day 1 Treatment Session I	Day 22 (\pm 3 Days) Treatment Session II	Day 43 (\pm 3 Days) Treatment Session III	Day 71 (\pm 10 Days)	Day 85 (\pm 5 Days)/ Biopsy Follow-up	Day 161 (\pm 15 Days)	Day 251 (\pm 15 Days)/ Early Termination	Day 265 (\pm 5 Days)/ Biopsy Follow-up
MRI		X ^g Dimples 1, 2, and 3					X ^h Dimples 2 and 3			X ^h Dimple 3	
Biopsy sample collection			X ⁱ Dimple 1				X ^j Dimple 2			X ^j Dimple 3	
Biopsy follow-up examination				X				X ^k			X ^k
Select and mark up to 12 dimples for CCH injection in each treatment area (including Dimples 2 and 3)				X	X	X					
Study drug administration				X	X	X					
Concomitant medications	X	X	X	X	X	X	X	X	X	X	X
Injections site reactions/local tolerability in areas treated				X	X	X	X		X	X	
All other AEs ^l	Monitored throughout the study										

^a Performed prior to any study-required assessments, unless exceptions granted for standard of care procedures. A separate informed consent may be used for HIV testing and must be signed before the sample is collected, if required.

^b Should be reassessed and verified prior to dosing.

^c Vital signs will be collected up to 4 hours prior to, and at 15 and 30 minutes after, study treatment administration on Days 1, 22, and 43.

^d Urine pregnancy test should be completed prior to the MRI.

^e At screening all 4 potential treatment areas (each buttock and each thigh) will be imaged; and CR-PCSS, PR-PCSS, and Hexsel CSS assessments will be done for each potential treatment area (each buttock and each thigh).

^f Before and after marking dimples for treatment. No manipulation of the treatment area should be done prior to the “before” photographs.

^g Screening MRIs will be performed after all other screening assessments (except the biopsy) have been completed. MRIs may be repeated within the screening window as often as necessary to obtain evaluable images.

^h The Day 71 and Day 251 MRIs may be performed up to 7 days prior to the indicated visit. The MRI must be completed before the biopsy required for these visits. The Day 251/Early Termination MRI is not required for subjects who withdraw from the study (early termination). The Day 71 and Day 251 MRIs may be repeated as often as necessary to obtain an evaluable image.

Table 1: Schedule of Activities (Continued)

ⁱ The screening biopsy will be performed after all other screening assessments (including MRI) are completed. The screening biopsy will be performed at least 14 days prior to the Day 1 Treatment Visit. The investigator must examine and confirm sufficient healing of the biopsy site before dosing on Day 1. The timing of all subsequent visits will be based on the actual date that the first dose of CCH is administered.

^j The Day 71 and Day 251 imaging for efficacy, PR-PCSS, and CR-PCSS must be completed prior to the biopsy sample collection required at those visits. The Day 251/Early Termination biopsy is not required for subjects who withdraw from the study (early termination). For subjects who received less than 3 doses of CCH prior to 18 March 2020, no Day 71 or Day 251 biopsy samples will be collected.

^k Visit not required for subjects who had less than 3 doses of CCH prior to 18 March 2020.

^l Adverse events (AE)/serious adverse events (SAE) will be captured from time of informed consent signature until the Day 265 Visit or until 28 days after last dose of study drug whichever is later. There is no time limit on collection of SAEs considered to be related to study treatment.

Note: Unless otherwise stated above or outlined below (and with the exception of injection site reactions/local tolerability in the areas treated), all assessments should be completed prior to dosing on treatment days (Days 1, 22, and 43).

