8.2.9. Biopsy Follow-up Examination

The investigator will examine the biopsy site for evidence of ongoing AEs related to the biopsy and to determine if the biopsy site has healed at times specified in the Schedule of Activities (Section 1.2). The Day 85 and Day 265 Biopsy Follow-up Visits are not required for subjects who had less than 3 doses of study drug prior to 18 March 2020.

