3. STUDY DESIGN AND MEASURES

3.1. Study Design

This is a single center, open-label, Phase 2a study to assess the safety and efficacy of CCH in adult women with moderate or severe edematous fibrosclerotic panniculopathy (EFP) of the buttocks or thighs using photonumeric scales, MRI, and histopathology of tissues from the treated area. Approximately 18 subjects will be screened in order to dose approximately 12 subjects. Every attempt will be made to enroll an equal number of subjects across the 2 severity levels in both buttocks and thighs (eg, 3 subjects with moderate buttock cellulite, 3 subjects with severe buttock cellulite, 3 subjects with moderate thigh cellulite, and 3 subjects with severe thigh cellulite).

Following a screening period of approximately 35 days, qualified subjects will receive 0.84 mg of CCH per treatment area (buttock or thigh) for a total dose of 1.68 mg in both buttocks or both thighs per treatment session for 3 sessions. Treatment sessions will occur approximately 21 days apart (Day 1, Day 22, and Day 43). Following treatment and assessments at Day 71, subjects will be assessed and followed for an additional 194 days.

Statistical Analysis Plan (SAP) Module 1 – Protocol EN3835-212

Subjects will have MRIs and double punch biopsies of 3 selected target dimples 3 times during the study (Screening, Day 71, and Day 251).

Subjects will participate in the study for up to approximately 305 days (approximately 10 months). The duration of the study from first subject first visit to last subject last visit will be dependent upon the ability of the site to identify and enroll subjects. The entire study is expected to require approximately 12 months to complete.

Table 2 below describes the schedule of activities and assessments performed during screening, the treatment phase, and the extension phase of the study.

Table 2: Schedule of Activities

Activities	Screening (Day -35 to Day -1)			Treatment Phase				Extension Phase			
	Before MRI	Before biopsy	Approximately Day -14	Day 1 Treatment Session I	Day 22 (± 3 Days) Treatment Session II	Day 43 (± 3 Days) Treatment Session III	Day 71 (+10 Days)	Day 85 (±5 Days)/ Biopsy Follow-up	Day 161 (± 15 Days)	Day 251 (±15 Days)/ Early Termination	Day 265 (±5 Days)/ Biopsy Follow-up
Informed consent ^a	X										
Inclusion/exclusion criteria review ^b	X			X							
Medical and surgical history	X										
EFP history	X										

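### Because visits run from the first dose, a late Day 251 biopsy can be followed within days by its Day 265 check, the last scheduled visit; tying that check to the biopsy date is a cheap, minor improvement.

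*Protocol*

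**What the plan says.** Protocol 1.2, footnote i, sets one anchor for everything after Day 1: "The timing of all subsequent visits will be based on the actual date that the first dose of CCH is administered". The schedule, most legible in SAP Table 2, gives the Dimple 3 biopsy visit as "Day 251 (±15 Days)/ Early Termination" and its check as "Day 265 (±5 Days)/ Biopsy Follow-up". Protocol 8.2.9 gives the check two purposes, to look for biopsy-related adverse events (AEs) and "to determine if the biopsy site has healed at times specified in the Schedule of Activities". For timing it only points back to the schedule. SAP 3.13.9 likewise lists visit days and no interval.

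For the screening biopsy, footnote i does state an interval: "The screening biopsy will be performed at least 14 days prior to the Day 1 Treatment Visit". There is no counterpart for the Day 251 biopsy. Footnote h adds two rules on sequence: "The MRI must be completed before the biopsy required for these visits", and "The Day 71 and Day 251 MRIs may be repeated as often as necessary to obtain an evaluable image".

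AE collection runs, by footnote l, "until the Day 265 Visit or until 28 days after last dose of study drug whichever is later". Protocol 8.3.1 and 10.3.4.1 also take it to the Day 265 Visit for subjects who do not terminate early.

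**The concern.** The visit numbers suggest that the biopsy site is looked at 14 days after the procedure. With both visits timed from the first dose and given independent windows, that spacing is not protected. The biopsy window is also three times as wide as the check window (±15 against ±5 days), so the biopsy can drift late while the check stays put.

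The plan gives the site no compliant way to wait. Protocol 8 requires adherence to the schedule and rules out waivers, and SAP 4.2 names an out-of-window visit as a possible deviation. A site that checks a Day 266 biopsy on Day 267 complies. A site that waits 14 days does not.

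No scheduled visit follows. At stake are the value of the healing check and the even capture of new or late non-serious biopsy-site events. The photonumeric, MRI and histology results are unaffected.

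**Working it through.** **Inputs**
- Biopsy day B: 251 ± 15, so Days 236 to 266, which is 31 window days (Protocol Table 1, SAP Table 2).
- Check day C: 265 ± 5, so Days 260 to 270 (same tables).
- Both are counted from the first dose (footnote i).
- Third dose: Day 43 ± 3, so Day 46 at the latest.

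**Nominal interval.** 265 − 251 = 14 days. The visit labels imply this figure; the plan does not state it as an interval.

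**Range of gaps.** Longest gap = 270 − B. Shortest gap, with the check on or after the biopsy, = max(260, B) − B.

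| Biopsy day | Shortest gap | Longest gap |
|---|---|---|
| 236 | 24 | 34 |
| 251 | 9 | 19 |
| 256 | 4 | 14 |
| 257 | 3 | 13 |
| 261 | 0 | 9 |
| 262 | 0 | 8 |
| 266 | 0 | 4 |

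**Thresholds**
- 14 days is out of reach when 270 − B < 14, so B > 256: Days 257–266, 10 of 31 window days.
- 9 days is out of reach when 270 − B < 9, so B > 261: Days 262–266, 5 of 31.
- A check less than 9 days after the biopsy is permitted, though not forced, when 260 − B < 9, so B > 251: Days 252–266, 15 of 31.
- The two windows overlap on Days 260–266.

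These are counts of window days, not probabilities.

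**Which limit ends AE collection.** The latest on-schedule last dose plus 28 days is 46 + 28 = Day 74. The earliest Day 265 Visit is Day 260. The visit is therefore the operative end of active collection of new non-serious AEs.

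**Subjects concerned.** The 12 new subjects, plus up to 2 who had all three doses before 18 March 2020 and for whom the biopsies are optional (Protocol 2.1, 8.6.2): 12 + 2 = 14 at most. Subjects with fewer than three doses before that date have no Day 251 biopsy, and it is not required of those who terminate early (footnote j). If the interim analysis finds no identifiable change, later biopsies stop (9.4) and the number falls, possibly to zero.

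**Day 71 biopsy, for comparison.** The latest biopsy is Day 81 and the latest Day 85 check is Day 90, so 90 − 81 = 9 days can always be reached. Visits at Days 161 and 251 follow. It is not counted here.

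**The case against.** The arithmetic is hard to dispute. The case against concerns consequence, and much of it stands.

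- **Follow-up of open events.** A reader might infer that any non-serious problem still open at the last visit is simply dropped. The documents do not support that. Protocol 8.3.3 follows recorded non-serious AEs of special interest (AESIs) to resolution or stabilization. Under 8.3.7 these include local injection-site events, and Dimple 3 is injected at every session. Whether a biopsy-site event some 200 days after the last injection would qualify is arguable. What remains is non-AESI events and events that appear after the visit.
- **Serious events and extra visits.** Serious events related to treatment or study participation stay reportable (footnote l, 8.3.1), and 8.2 allows unscheduled safety assessments. The first covers serious events only; the second is optional.
- **The 14-day benchmark.** A reader might infer that the plan breaches its own healing standard. It does not: the 14 days after the screening biopsy precede dosing, and no dose follows the Day 251 biopsy. The documents give no healing time for an 8 mm double punch, so they cannot show that 4 days is inadequate or 9 adequate.
- **Late biopsies.** A reader might infer that repeat MRIs will push biopsies to the end of the window. Footnote h also allows the MRI up to 7 days before the visit, which leaves room for repeats. Nothing suggests that biopsies will cluster on Days 262–266.
- **Early Termination.** A reader might infer that a subject who withdraws soon after the Day 71 biopsy leaves with the site unassessed. Local tolerability in the treated areas is already scheduled at that visit, AEs are recorded, and 7.1 encourages dosed subjects to complete the remaining visits. Only an explicit biopsy-site examination is unlisted.
- **An unseen manual.** Protocol 8.6.2 places detailed biopsy directions in the Clinical Operations Study Manual. The absence of a link between biopsy and check is established only for the Protocol and SAP.

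**Conclusion.** The point holds as a minor safety and scheduling weakness. The permitted extreme is a check at most 4 days after the biopsy, against a nominal 14, at the subject's last scheduled visit. The gap concerns the healing check itself and new or late non-serious biopsy-site events that are not AESIs.

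The conclusion rests on the windows as printed, on timing from the first dose, and on no overriding instruction in the study manual. It assumes nothing about how often biopsies run late or how long healing takes. With few subjects, several existing safeguards and no effect on efficacy results, this is a worthwhile clarification and not a condition for the trial to proceed.

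**What to change.** In footnote i, Table 1 and Protocol 8.2.9, with SAP Table 2 and SAP 3.13.9 aligned: when the Day 251 biopsy is done after Day 251, hold the Day 265 Visit at biopsy date + 14 (±5) days; otherwise keep Day 265 (±5). AE collection runs to that visit.

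**Effect.** For B ≤ 251 the gap is at least 260 − 251 = 9 days. For B > 251 it is 9 to 19 days. The minimum is therefore 9 on all 31 window days. No subject leaves before Day 260, as now, and no visit is added.

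**Cost.** The last visit may fall as late as 266 + 19 = Day 285, so participation may reach 35 + 285 = 320 days against 35 + 270 = 305. A visit past Day 270 is forced only when B + 9 > 270, that is, for biopsies on Days 262–266. Matching edits are needed to the 305-day statements (Protocol 1.1, 4.1), the Day 265 limits in 8.2.8 and 10.3.4.2, and the 194-day statement in SAP 3.1.

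**Limit.** This does not by itself extend follow-up of non-AESI events still open at the last visit. Section 10.3.4.1 would still end it there, and 8.3.1 ends it at resolution or 28 days after the last treatment, whichever comes first.

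**Optional.** At an Early Termination visit, add an explicit look at any biopsy site not yet checked.
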